### **3.9.1.1 Overall Summary of Treatment Emergent Adverse Events**

An overall summary of TEAEs will be presented by cohort and for all subjects combined. The number and percentage of subjects who experienced at least one AE, at least one TEAE, at least one TRAEs, at least one TEAE of Grade 3 or higher, at least one TRAE of Grade 3 or higher, at least one serious TEAE, at least one DLT, at least one serious TRAE, at least one TEAE leading to treatment discontinuation, at least one TRAE leading to treatment discontinuation, and number of subjects with an adverse event resulting in death will be displayed.

### **3.9.1.2 Treatment Emergent Adverse Event Incidences**

The incidence of TEAEs will be presented by cohort and for all cohorts combined. The number and percentage of subjects who experienced at least one TEAE as well as the number and percentage of subjects who experienced at least one TEAE within each specific SOC and PT will be presented. For this analysis, if a subject has more than one occurrence of the same PT, then the PT will be counted only once for that subject. Similarly, if a subject has more than one PT within the same SOC, the subject will be counted only once in that SOC.

A summary table of TEAEs by PT will also be presented by cohort and for all cohorts combined.

For the presentation of AE incidences, the SOCs will be sorted alphabetically, and within SOC, the preferred term (PT) will be presented by decreasing total frequency.

Adverse events leading to study withdrawal, leading to study drug interruption or discontinuation, treatment emergent adverse events, serious adverse events, dose-limiting toxicities, and deaths will be displayed in subject listings.

### **3.9.1.3 Adverse Events by Maximum CTCAE Grade**

TEAEs will be presented by maximum CTCAE grade for each PT by cohort and for all subjects combined. For this analysis, if a subject has more than one occurrence of the same PT, then the PT will be counted only once for that subject under the maximum grade at which it was experienced.

### **3.9.1.4 Treatment Related Adverse Events**

Adverse events with a relationship to study drug of “possibly,” “probably” or “definitely” related will be classified as treatment related.

The number and percentage of subjects who experienced at least one treatment related AE within each specific SOC and PT will be presented overall and by cohort. For the presentation of AE incidences, the SOCs will be sorted alphabetically, and within SOC, the preferred term (PT) will be presented by decreasing total frequency.

The incidences of adverse events related to MEDI4736, motolimod, and PLD will also be summarized by SOC and PT.

Incidence of treatment related AEs will be presented by maximum CTCAE grade for each PT by cohort. For this analysis, if a subject has more than one occurrence of the same PT, then the PT will be counted only once for that subject under the maximum grade at which it was experienced.

The incidences of adverse events related to MEDI4736, motolimod, and PLD will also be presented by maximum CTCAE grade for each PT overall and by cohort.

### **3.9.1.5 TEAEs Leading to Study Drug Withdrawal**

TEAEs leading to study drug withdrawal of MEDI4736, motolimod, or PLD will be presented by SOC and PT and will also be presented in a subject listing.

### **3.9.1.6 DLTs**

DLTs will be presented in subject listings.

### **3.9.1.7 Serious Adverse Events**

The incidences of serious adverse events will be summarized by SOC and PT overall and by cohort. SAEs will be presented in a subject listing.

### **3.9.2 Clinical Laboratory Evaluation**

For each continuous laboratory (hematology and chemistry) parameter, results will be categorized as low, normal, or high based on the laboratory normal ranges.

Frequencies and percentages will be presented by cohort and overall for the shifts in these categories from baseline to selected post-treatment assessment time points (i.e., low to normal, low to high, high to low, etc.). Percentages for the shift tables will be calculated based on the number of subjects who had results for both baseline and the corresponding post-treatment assessment time point. Additionally, for continuous hematology and chemistry parameters, descriptive statistics will be presented for the changes from baseline to each selected post-treatment assessment time point.

Abnormal laboratory values with their clinical significance status will be presented in a subject listing.

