4.2.2 Subject Evaluation & Statistics

The Per-Protocol (PP) Population for DLT Assessment includes:

- All subjects who experience a DLT at any time during the DLT Evaluation Period (as defined in Section 3.1.9)
- All subjects with no DLT who receive at least 75% of the scheduled doses of MEDI4736, motolimod (pre Amendment 2), and PLD as well as respective safety assessments, without major protocol violations, over the entire DLT Evaluation Period (as defined in Section 3.1.9).

Refer to Section 3.1.11 for subject replacements.

The Intent-To-Treat (ITT) Population for safety and tolerability is defined as all subjects who receive at least one dose of PLD, motolimod (pre Amendment 2) or MEDI4736.

In Phase 1, for the primary endpoint of determining DLTs and the MTD, the analysis of safety and tolerability will be based on the PP Population for DLT Assessment.

In both Phases 1 and 2, the overall analysis of safety and tolerability will be based on the ITT Population for safety and tolerability.

Appropriate summaries of AEs, laboratory data and vital sign data will be presented. Adverse events will be coded using the MedDRA dictionary. Incidences of treatment-emergent adverse events (TEAE, those events that started after dosing or worsened in severity after dosing) will be presented overall and by maximum severity (according to CTCAE version 4.03) and relationship to study medication.

For each continuous laboratory parameter, results will be categorized as low, normal, or high based on the laboratory normal ranges. Frequencies and percentages will be presented by treatment arm for the shifts in these categories (i.e., low to normal, low to high, high to low, etc.) from baseline to each post-treatment assessment time point. Additionally, for each continuous hematology and chemistry parameter, descriptive statistics will be presented by treatment arm for the changes from baseline to each post-treatment assessment time point. Descriptive statistics will be presented by cohort for the changes in vital signs from baseline to each post-treatment assessment time point.

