6.	
Laboratory parameters for vital functions should be in the normal range. Laboratory abnormalities that are not clinically significant are generally permitted, except for the following laboratory parameters, which must be within the ranges specified, regardless of clinical significance:
 
 
 Hemoglobin	≥ 9 g/dL	
 
 Neutrophil count	≥ 1.5 x 10⁹/L	
 
 Platelet count	≥ 100,000/mm³	
 
 Serum creatinine, or Creatinine Clearance	≤ 1.5x Institutional Upper Limit of Normal (ULN), or ≥ 50 mL/min (by Cockcroft-Gault formula)	
 
 Serum bilirubin	≤ 1.2 mg/dL	
 
 AST/ALT	≤ 2.5 x ULN	
 
 Alkaline phosphatase	≤ 2.5 x ULN	
 
	Hemoglobin	≥ 9 g/dL	Neutrophil count	≥ 1.5 x 10 ⁹ /L	Platelet count	≥ 100,000/mm ³	Serum creatinine, or Creatinine Clearance	≤ 1.5x Institutional Upper Limit of Normal (ULN), or ≥ 50 mL/min (by Cockcroft-Gault formula)	Serum bilirubin	≤ 1.2 mg/dL	AST/ALT	≤ 2.5 x ULN	Alkaline phosphatase	≤ 2.5 x ULN
Hemoglobin	≥ 9 g/dL														
Neutrophil count	≥ 1.5 x 10 ⁹ /L														
Platelet count	≥ 100,000/mm ³														
Serum creatinine, or Creatinine Clearance	≤ 1.5x Institutional Upper Limit of Normal (ULN), or ≥ 50 mL/min (by Cockcroft-Gault formula)														
Serum bilirubin	≤ 1.2 mg/dL														
AST/ALT	≤ 2.5 x ULN														
Alkaline phosphatase	≤ 2.5 x ULN														
7.	Age ≥18 years.														

CONFIDENTIAL

8.	Able and willing to give valid written informed consent.
9.	Body weight > 30 kg

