#### **3.1.2 Reporting of Numerical Values**

All clinical study data will be presented in subject data listings. All by-visit summarizations will be conducted using data from Cycle 1, Cycle 2, and/or the last cycle, as applicable. All data presentations will be by the planned cohorts in the protocol, separately for Phase 1 and Phase 2.

Descriptive statistics (n, mean, standard deviation, median, minimum and maximum) will be calculated by cohort for continuous variables.

Frequencies and percentages will be presented by cohort for categorical and ordinal variables. If there are missing values, the number missing will be presented, but without a percentage.

Means and medians will be reported to one decimal place more than the data reported in the EDC. Standard deviations will be reported to two decimal places more than the data reported. Minimum and maximum will be reported to the same number of decimal places captured in the EDC.

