#### **3.1.3 Baseline Value and Change from Baseline**

Baseline value is defined as the most recent non-missing value obtained immediately prior to administration of first dose. Change from baseline will be calculated by subtracting the baseline value from the post-treatment assessment for each subject (i.e., post-treatment – baseline).

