#### **3.1.5 Handing of Repeated Assessments**

If multiple results are available for a test at the same scheduled time point post-baseline then the following rules will be used:

- If multiple pre-dose assessments are available at the same scheduled time point and all results are considered normal, then the first (earliest) result will be used in all summarizations.
- If multiple pre-dose assessments are available at the same scheduled time point and at least one result is considered abnormal, then the worst (most abnormal) result will be used in the summarization.

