## **3.9 Safety Analysis**

All safety analyses will be performed using the ITT population. For clinical laboratory, data collected from all core study cycles and/or on-study follow-up assessments will be analyzed for each subject. For vital signs, ECOG performance status, and ECG, only data collected from the first two cycles and/or on-study follow-up assessments will be analyzed for each subject. All subject data including those from the additional cycles will be presented in subject listings.

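### The laboratory tables in SAP 3.9.2 cannot count Grade 3–4 values or the protocol's joint hepatic criterion, and SAP 3.1.2 and 3.9 conflict on which visits they cover

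*SAP*

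**What the plan says.** **Categories.** SAP 3.9.2 plans two summaries for haematology and chemistry. In the first, "results will be categorized as low, normal, or high based on the laboratory normal ranges" and shifts are tabulated "from baseline to selected post-treatment assessment time points". The second is descriptive change from baseline, also at selected time points. The list of tables has only Tables 14.4.1 to 14.4.4 for laboratory data. None is by CTCAE grade, none is by worst post-baseline value, and none combines liver parameters.

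**Protocol counterpart.** Protocol 4.2.2 uses the same three categories and the same change summaries, but at every visit: "low to normal, low to high, high to low, etc.) from baseline to each post-treatment assessment time point".

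**Visits.** Two SAP sections bear on what *selected* means. SAP 3.1.2: "All by-visit summarizations will be conducted using data from Cycle 1, Cycle 2, and/or the last cycle, as applicable". SAP 3.9: "For clinical laboratory, data collected from all core study cycles and/or on-study follow-up assessments will be analyzed for each subject".

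**Worst value.** SAP 3.1.5 has a rule for repeated results, "then the worst (most abnormal) result will be used in the summarization", but it chooses among pre-dose results at one scheduled time point, not across visits.

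**Entry values.** Protocol 5.1, criterion 6: "Laboratory abnormalities that are not clinically significant are generally permitted, except for the following laboratory parameters, which must be within the ranges specified". Those ranges admit AST, ALT and alkaline phosphatase up to 2.5 × ULN and creatinine up to 1.5 × ULN.

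**Severity elsewhere.** Protocol 4.2.1 and SAP 2.2.4 have clinically significant laboratory abnormalities recorded as adverse events and graded by CTCAE v4.03. SAP 3.9.1.3 tabulates treatment-emergent events by maximum grade. Abnormal values are listed with their clinical significance status.

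**The concern.** A three-way split shows whether a value left the normal range, not how far. Subjects may enter with raised liver enzymes or creatinine, and for them worsening produces no shift at all. Safety is the primary objective of Phase 1 and a secondary objective of Phase 2. The special-interest events for MEDI4736 include hepatic, renal and pancreatic toxicity. A reader of the report will want the number of subjects who reached Grade 3–4 values and the number who met the protocol's own hepatic criterion. The laboratory tables cannot give either number, and two SAP rules disagree on which visits the tables cover.

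**Working it through.** The documents state no figure on this point, so there is none to reproduce. The check applies the SAP rule to values taken from the protocol.

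**1. What the shift table shows.** Inputs: the entry limit for ALT of 2.5 × ULN (Protocol 5.1), and 5 × ULN as the upper limit of Grade 2 for transaminases, with 8 × ULN as a further threshold (Protocol 3.1.9).

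- 2.5 to 2.6 × ULN: high to high.
- 2.5 to 5.1 × ULN (Grade 3 or higher): high to high. The 5 × ULN bound is reached by a 5 / 2.5 = 2.0-fold rise.
- 2.5 to 8 × ULN: high to high, an 8 / 2.5 = 3.2-fold rise.
- 0.8 to 1.1 × ULN and 0.8 to 6 × ULN: both normal to high.

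The same holds for AST, alkaline phosphatase and creatinine without any grade threshold, because a value already above ULN stays high however far it rises. For platelets the result depends on the local lower limit, which the documents do not give. If that limit is above 100,000, a fall from 100,000 (eligible) to 49,000 (Grade 3 in Protocol 8.2.1) is low to low. No figure is claimed for haemoglobin, or for bilirubin, which is capped at 1.2 mg/dL at entry.

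**2. What the adverse event tables add.** The maximum-grade tables hold a laboratory value only once it has been recorded as an adverse event. Protocol 4.2.1 and SAP 2.2.4 require this only when the value is judged clinically significant. Protocol 3.1.9 foresees a pre-existing abnormality reaching Grade 3/4 with the deterioration judged not clinically significant. That is a Phase 1 DLT exception needing both Investigator and Sponsor, not a rule on recording, but it shows that grade and judged significance can part.

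**3. The hepatic criterion.** Protocol 7.1.8 defines it as ALT or AST > 3 × ULN with total bilirubin > 2 × ULN, from one draw or from draws within 8 days. Single-parameter shift tables cannot show a joint event. On the main schedule, draws fall on Days 1 and 3, so the next scheduled draw after Day 3 is nominally 26 days later (Day 3 to Day 29). With every window against it, this is 26 − 3 − 1 − 3 = 19 days, still more than 8. Any other pair of separate draws within 8 days therefore needs an unscheduled draw, so a count has to use all values.

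**4. Visits.** Baseline is fixed by SAP 3.1.3: "Baseline value is defined as the most recent non-missing value obtained immediately prior to administration of first dose". The pre-dose Cycle 1 Day 1 sample is therefore baseline, not a post-treatment time point.

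| | Main schedule | Dose level 0a |
|---|---|---|
| Draws over 12 cycles | 2 × 12 = 24 | 3 × 12 = 36 |
| Less Cycle 1 Day 1 | 23 | 35 |
| Plus 3 follow-up visits (Protocol 4.2.2, *each*) | 26 | 38 |
| On-treatment points left by SAP 3.1.2 (Cycles 1, 2 and 12) | 2 × 3 − 1 = 5 | 3 × 3 − 1 = 8 |

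Read literally, SAP 3.1.2 drops Cycles 3 to 11, which SAP 3.9 and Protocol 4.2.2 keep.

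**The case against.** The case against is substantial.

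- **The SAP follows the protocol.** Protocol 4.2.2 sets the three categories, and neither document promises a laboratory grade table. The Phase 2 safety endpoint, toxicity by CTCAE, is met by the graded adverse event tables. The SAP document history shows that version 2.0 took out references to CTCAE grades for laboratory data, so the omission is a choice. This stands: a reader might infer a breach of protocol in the missing grades, and the documents do not support that.
- **Visits are addressed.** A reader might infer from *selected* that the time points are undefined. They are not: SAP 3.1.2 and 3.9 both speak to them, and 3.9 is the specific rule for laboratory data. What remains is a conflict between the two, softened but not settled by the wording *as applicable* in 3.1.2.
- **Severity is largely captured.** Severe values usually prompt action. Asymptomatic Grade 3 or 4 amylase or lipase means holding MEDI4736, and in hepatitis transaminases > 8 × ULN mean stopping it (Protocol 8.4.2.1). Many such values would be recorded as adverse events. Change tables give minimum and maximum, and with about 53 planned subjects the listings can be counted by hand. This stands in part: minimum and maximum show one extreme per time point rather than a number of subjects, and a hand count is not a planned output.
- **Hepatic events can be counted by preferred term.** Protocol 7.1.8 treats hepatic function abnormality as an event of special interest, and adverse events are recorded whatever their severity or cause (7.1.5). A reader might infer that cases with a confirmed unrelated diagnosis drop out of the data. The exemption in 7.1.2.3, like the phone or email route in 7.1.2, concerns only the 24-hour report. A preferred-term count still depends on how the event is entered and coded; a count from laboratory values does not.

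**Conclusion.** The point holds as a cheap improvement to descriptive safety reporting. Apart from the visit-rule conflict, it is not an error in the plan.

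The laboratory tables cannot separate Grade 1 from Grade 3–4, cannot show worsening from a permitted abnormal baseline, and cannot show the joint hepatic criterion. The adverse event tables fill the gap only for values judged clinically significant or entered under a hepatic term. The visit conflict needs resolving, because SAP 3.1.2 read literally leaves out the middle nine cycles.

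The number of affected subjects is unknown, since the documents give no rate of abnormal baselines. It would be too strong to say that severe laboratory toxicity will go unreported: the text shows a possible gap in counting and no affected subject. The primary efficacy test is not affected. The results for AST, ALT, alkaline phosphatase and creatinine rest on the eligibility text alone; the platelet example rests on an assumed local lower limit above 100,000.

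**What to change.** Keep the present tables. In SAP 3.9.2, for the ITT population by cohort and overall:

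1. Add a table of baseline against worst post-baseline CTCAE v4.03 grade for key parameters: neutrophils, platelets, haemoglobin, ALT, AST, alkaline phosphatase, total bilirubin, creatinine, amylase and lipase. Use all post-baseline values, unscheduled ones included. Extension-phase values go beyond the scope that SAP 3.9 sets for laboratory analysis, so their inclusion should be stated explicitly.
2. Add a count of subjects with ALT or AST > 3, > 5 and > 8 × ULN, with bilirubin > 2 × ULN, and with ALT or AST > 3 × ULN plus bilirubin > 2 × ULN within 8 days.
3. State that SAP 3.9 governs laboratory data over SAP 3.1.2, and replace *selected* with *each* core-study and follow-up time point.

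Cost: SAP wording, programming for two tables, and bringing back laboratory grading, references to which version 2.0 removed. The values and normal ranges are already collected, so no new assessments are needed.

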### **3.9.3 Vital Signs**

For vital signs, descriptive statistics will be presented for changes from pre-dose to end of infusion on MEDI4736 dosing days in the first two cycles and for On Study Follow-up assessments. End of infusion time points and change from pre-dose to end of infusion for subjects who experienced an interruption in the study drug administration (administration was stopped and subsequently restarted) will not be included.

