3.1.8 Dosing Adjustments, Delays and Discontinuations

PER Amendment 2, motolimod dosing will be discontinued for all subjects.

Dose adjustment and management guidelines for toxicity related to the standard PLD regimen, motolimod, and MEDI4736 are outlined in Sections 8.2, 8.3, 8.4, respectively.

In the event of a delay in PLD dosing due to drug-related toxicity, doses of motolimod and MEDI4736 should also be delayed, so that the relative timing of the administration of each drug within each cycle is not altered. That is, the administration of PLD always constitutes cycle Day 1, and the dose dates of motolimod and MEDI4736 are determined relative to this date (see Section 3.1.7). Note that delays in the dosing of motolimod or MEDI4736 due to drug-related toxicity should not delay the 28-day dosing cycle of PLD, if possible. Likewise, any delay in MEDI4736 should not delay the administration of motolimod, and vice versa.

If PLD has to be discontinued due to PLD-related toxicities, the treatment with motolimod and/or MEDI4736 may continue, provided that the subject had received at least 2 doses of PLD (i.e., 2 cycles).

Irrespective of delay(s) in the dosing of the combination treatment, the disease assessments (CT, MRI) should not be delayed and must be conducted on the days originally scheduled, as calculated from the first study dose of PLD (Cycle 1 Day 1).

If a toxicity occurs that requires toxicity management in accordance with the toxicity management guidelines referenced above, and the toxicity causing drug can be clearly identified, then the respective guideline should be followed. If the toxicity causing drug cannot be identified, then the more conservative guideline should be followed.

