### 3.3.2 Safety Variables

Safety variables include:

- Incidence of treatment emergent adverse events (TEAEs), defined as an adverse event (AE) that is first identified, or is identified to worsen in intensity, at a time point occurring after the first dose of study drug
  - All TEAEs by System Organ Class (SOC) and Preferred Term (PT)
  - All TEAEs by PT
  - TEAEs by maximum severity (according to CTCAE version 4.03)
  - Treatment related TEAEs (TRAЕ) defined as events with a relationship to any study drug of ‘Definitely Related’, ‘Probably Related’ or ‘Possibly Related’
  - Treatment related TEAEs by maximum severity (according to CTCAE version 4.03)
  - TEAEs leading to study drug withdrawal
  - Serious TEAEs
- Change in clinical laboratory parameters (hematology, chemistry, amylase, lipase, thyroid) from baseline to each selected post-treatment assessment time point and shifts in clinical laboratory parameters from baseline to each selected post-treatment assessment time point
- Change in vital signs (systolic and diastolic blood pressure, heart rate, respiratory rate, and body temperature) from pre-dose to end of infusion at selected post-treatment assessment time points
- Change in ECOG performance status from baseline to last assessment
- Shifts in ECG from baseline to each selected post-treatment assessment time point

- Shifts in ECHO or MUGA from baseline to each selected post-treatment assessment time point

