Table 14.3.6.4	Incidence of Pegylated Liposomal Doxorubicin (PLD) Related Adverse Events By Maximum CTCAE Grade, MedDRA System Organ Class and Preferred Term, ITT Population
Table 14.3.7.1	Incidence of Treatment Related Adverse Events Leading to MEDI4736 Withdrawal by MedDRA System Organ Class and Preferred Term, ITT Population
Table 14.3.7.2	Incidence of Treatment Related Adverse Events Leading to Motolimod Withdrawal by MedDRA System Organ Class and Preferred Term, ITT Population
Table 14.3.7.3	Incidence of Treatment Related Adverse Events Leading to PLD Withdrawal by MedDRA System Organ Class and Preferred Term, ITT Population
Table 14.3.8	Incidence of Serious Adverse Events by MedDRA System Organ Class and Preferred Term, ITT Population
Table 14.4.1	Hematology Parameters – Change from Baseline, ITT Population
Table 14.4.2	Hematology Parameters – Shift from Baseline, ITT Population
Table 14.4.3	Chemistry Parameters – Change from Baseline, ITT Population
Table 14.4.4	Chemistry Parameters – Shift from Baseline, ITT Population
Table 14.4.5	Vital Signs – Change from Pre-dose to End of Infusion, ITT Population

Table 14.4.6	ECOG Performance Status at Baseline and Last Assessment, ITT Population
Table 14.4.7	ECG-Shift from Baseline, ITT Population
Table 14.4.8	ECHO or MUGA-Shift from Baseline, ITT Population

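### The SAP replaces the protocol's vital-sign change from baseline with a within-infusion change and gives no reason, so no planned summary shows change from baseline at any post-baseline visit

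*SAP*

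**What the plan says.** Protocol 4.2.2 states the planned presentation: "Descriptive statistics will be presented by cohort for the changes in vital signs from baseline to each post-treatment assessment time point".

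The SAP plans something else in three places:

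- SAP 3.3.2 lists the safety variable as vital-sign change "from pre-dose to end of infusion at selected post-treatment assessment time points".
- SAP 3.9.3 calls for descriptive statistics for "changes from pre-dose to end of infusion on MEDI4736 dosing days in the first two cycles and for On Study Follow-up assessments".
- Table 14.4.5, the only vital-sign table in the list of tables, is titled "Change from Pre-dose to End of Infusion, ITT Population".

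Two SAP rules also limit the visits. SAP 3.9 says: "For vital signs, ECOG performance status, and ECG, only data collected from the first two cycles and/or on-study follow-up assessments will be analyzed". SAP 3.1.2 confines by-visit summaries generally to Cycle 1, Cycle 2 and/or the last cycle. Everything else is listed only: "All subject data including those from the additional cycles will be presented in subject listings".

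SAP 3.1.3 does define a baseline: "Baseline value is defined as the most recent non-missing value obtained immediately prior to administration of first dose". The SAP uses change or shift from baseline for laboratory data (3.9.2), ECG (3.9.5) and ECHO/MUGA (3.9.6), but not for vital signs.

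**The concern.** The two documents measure different things. Change from baseline shows whether blood pressure, heart rate, respiratory rate or temperature has moved since treatment began. Change from pre-dose to end of infusion shows how a subject tolerates one infusion of about 60 minutes. The second cannot stand in for the first, because a shift that developed before the infusion is present in both readings and drops out of the difference.

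What is at stake is a descriptive safety presentation that the protocol promised. Without it, a modest but consistent drift across a cohort receiving an anthracycline with a checkpoint inhibitor would have no cohort-level estimate. A reader of the study report would have to reconstruct it from listings, or rely on investigators having judged individual values clinically significant. The SAP says that its methods are based on those in the protocol, yet gives no reason for this departure.

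**Working it through.** The plan states no sample size, power or error rate on this point, so there is no figure to reproduce. The check has three parts.

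**1. What each measure captures.** For one subject and one infusion, let B be the baseline value, P the pre-dose value and E the end-of-infusion value. Then

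E − B = (P − B) + (E − P).

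The protocol asks for change from B. The SAP tabulates only E − P, so the term P − B is not summarised anywhere.

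An example with assumed values: B = 120, P = 140, E = 140 mmHg. The SAP measure is 140 − 140 = 0, while the change from baseline is 140 − 120 = 20.

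A small simulation shows the same for a group. All its settings are assumptions: 41 subjects, baseline mean 120 with SD 12, within-subject noise SD 5, no acute infusion effect.

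| Sustained shift before pre-dose | Mean pre-dose to end of infusion | Mean baseline to pre-dose |
|---|---|---|
| 0 | −0.5 | −0.4 |
| 10 | −1.4 | 10.4 |
| 20 | 0.2 | 19.3 |

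**2. Whether the first infusion's pre-dose value could serve as baseline.** It cannot. Protocol 3.1.8 says that "the administration of PLD always constitutes cycle Day 1", and MEDI4736 follows on Day 3. Under SAP 3.1.3 baseline precedes the first dose, so the Cycle 1 Day 3 pre-dose reading is already post-baseline. No infusion change uses baseline as its reference.

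**3. Visit coverage.** Inputs are the two core-study flowcharts in Protocol 3.2, which mark vital signs at every treatment visit and at three On Study Follow-up visits. The Cycle 1 Day 1 pre-dose reading is taken as baseline, and the subject is assumed to complete 12 cycles.

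| | Outside level 0a | Level 0a |
|---|---|---|
| Treatment visits | 12 × 2 = 24 | 12 × 3 = 36 |
| Post-baseline treatment visits | 24 − 1 = 23 | 36 − 1 = 35 |
| With 3 follow-up visits | 23 + 3 = 26 | 35 + 3 = 38 |
| Visits with a planned infusion change | 2 (Day 3 of Cycles 1 and 2) | 4 (Days 3 and 17 of Cycles 1 and 2) |
| Visits with a planned change from baseline | 0 of 26 | 0 of 38 |
| Treatment visits after Cycle 2 (listed only) | 10 × 2 = 20 | 10 × 3 = 30 |

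Day 1 PLD visits are not MEDI4736 dosing days, so they enter no change summary.

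**Follow-up visits.** On Study Follow-up starts after the last study drug administration (Protocol 3.1.16), so nothing is infused. If 3.9.3 means an infusion change at those visits, the statistic has no inputs. If it means a summary of observed follow-up values, that can be done, but no reference value is named and no change from baseline results.

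**The case against.** The strongest case for the SAP is that the infusion-centred summary was a deliberate choice. The document history for version 2.0 records that detail on pre-dose and end-of-infusion records was added, and this matches the infusion monitoring in Protocol 6.3.5. As an analysis of infusion tolerance it is defensible. That stands, and it is why the infusion table should be kept. It does not explain why the protocol's presentation was dropped.

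A reader might infer more than the documents support, in three ways:

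- **That a protocol endpoint is lost.** The objectives table in Protocol section 4 gives the safety endpoints as DLT/MTD (Phase 1) and toxicity (Phase 2), by CTCAE. Vital-sign change is a specified descriptive presentation with no hypothesis attached.
- **That sustained changes are never examined.** Clinically significant abnormalities are recorded as adverse events and graded (Protocol 4.2.1, SAP 2.2.4), so they reach the adverse-event tables. All vital-sign values are listed (Listing 16.2.25). What is missing is a planned cohort-level summary.
- **That the follow-up analysis is impossible.** The repeated preposition in 3.9.3 allows follow-up assessments to be a separate object, summarised as observed values. The wording is ambiguous rather than certainly unworkable.

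The visit counts also describe a subject who completes treatment. With a 6-month PFS rate of 25% assumed for PLD alone (Protocol 3.1.6), many subjects may contribute fewer visits. That reduces the denominator, but the number of visits with a planned change from baseline remains zero.

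**Conclusion.** The point holds as an unexplained departure from a descriptive safety analysis that Protocol 4.2.2 specifies. The SAP's within-infusion change is planned at 2 of 26 post-baseline vital-sign visits (4 of 38 at dose level 0a), and change from baseline is planned at none. The counts assume 12 completed cycles on the current flowcharts, with Cycle 1 Day 1 pre-dose as baseline, and leave out the optional treatment extension. The cancellation of a pre-existing shift is an algebraic fact; the 10- and 20-unit shifts are illustrations, not expectations.

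This is a gap in safety reporting and should be corrected before the tables are produced. It has no bearing on the primary endpoint, alpha or power, or on the DLT and MTD determination.

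**What to change.** 1. In SAP 3.3.2, 3.9.3 and the list of tables, add a by-cohort table of vital-sign change from baseline, as defined in SAP 3.1.3. It should run to the pre-dose value at post-baseline treatment visits, including Day 1 PLD visits, and to each On Study Follow-up visit.
2. Amend the visit limits in SAP 3.9 and 3.1.2, which would otherwise contradict that table. Alternatively, state and justify a reduced set such as Cycles 1, 2, the last cycle and follow-up. For a subject completing 12 cycles this gives 1 + 2 + 2 + 3 = 8 of 26 visits outside level 0a and 2 + 3 + 3 + 3 = 11 of 38 at level 0a. Even this set needs SAP 3.9 extended to the last cycle for vital signs.
3. Keep the pre-dose to end-of-infusion change as a separate infusion-tolerance table, restricted to MEDI4736 dosing days, and reword 3.9.3 so that follow-up visits belong only to the change-from-baseline table.

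The cost is SAP wording and one extra table. The flowcharts already require all the readings, so no new data are needed.
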